## **Recruitment to the MSS3 host trial**

Potential participants will be identified from approximately 51 GP practices acting as Participant Identification Centres (PIC) across three research sites (Sheffield, Manchester and Gateshead). PIC sites will be recruited through local CRNs and Sheffield CTRU. A three-stage identification process will be adopted using computer searching, GP record screening and postal questionnaire.

**Stage 1:** The GP PIC sites will complete a computer search on the practice clinical system to identify patients whose records include: (a) at least one code for an MUS syndrome (e.g. irritable bowel syndrome, fibromyalgia) or at least two codes for negative investigations (e.g. CT Scan normal); (b) at least 2 referrals for specialist opinion or diagnostic investigations in the last 3 years; (c) no codes to indicate serious disease (e.g. cancer, coronary heart disease, inflammatory or connective tissue disease) which might account for a substantial number of symptoms.

**Stage 2:** Once the computer search has produced a list of patients a GP at the practice will screen the patient names (and where necessary their medical records) to exclude any patients with major medical conditions causing their symptoms which were not picked up on search and those for whom invitation by the practice may be inappropriate.

**Stage 3:** The standard recruitment pack will be posted to potential participants by their general practice. All those invited will receive: (1) an 'invitation to participate' letter, printed on the practice headed paper, (2) a standard length PIS (Appendix B outlines the standard length PIS), (3) an 'expression of interest' form, (4) a PHQ-15 questionnaire, and (5) a prepaid envelope addressed to Sheffield CTRU. Interested patients will return an expression of interest form and completed PHQ-15 to Sheffield CTRU, who will screen the PHQ-15 for eligibility.

#### Inclusion criteria - MSS3:

- 3. Aged between 18 69 years (inclusive) at the time of the computer search
- 4. Current physical symptoms which meet the below criteria
  - a. clinical records suggest MUS (presence of at least one code for an MUS syndrome or at least two codes for negative investigations)
  - b. records show at least 2 referrals for specialist opinion or diagnostic investigations in the last 3 years
  - c. records show no evidence of any previous or current major illnesses likely to cause multiple symptoms
  - d. doctors in the GP practice do not believe that the majority of the patient's symptoms can be currently explained by other pathology;

e. the score on the self-completed PHQ-15 symptoms scale is between 10 and 20 (inclusive)

### **Exclusion criteria – MSS3:**

- 7. A score of 3 on question 9 on the PHQ-9 completed at the baseline visit
- 8. Difficulty conducting a healthcare consultation in English without either a professional or family interpreter or other assistance (either indicated in GP records, or becoming apparent during the enrolment and consent process)
- 9. The GP regards inviting them to participate as inappropriate (e.g. recent bereavement)
- 10. Severe symptom-related disability (e.g. requiring help with daily personal care or severely impaired mobility)
- 11. Currently undergoing active multidisciplinary rehabilitation or specialist psychological treatment including specialist pain, fatigue or other symptom clinic.
- 12. Currently pregnant or less than 6 months postnatal at the time of the screening telephone call

Following stages 1-3, the details of interested and potentially eligible patients will be passed on to a local research nurse who will contact the patient to discuss the study further, answer any questions from the patient and discuss a timetable for further participation. If a potential participant wishes to proceed, the research nurse will complete screening checks by enquiring directly about the exclusion criteria relating to personal care, active multidisciplinary rehabilitation, and current specialist psychological treatment. When discussions are complete the researcher will make an appointment with the patient for study enrolment. If the patient wishes to have more time to consider participation then a second phone call can be arranged. Appendix A outlines the flow of participants in MSS3.

## Trial design: the factorial recruitment SWAT

Recruitment into the SWAT is planned to occur between October 2018 and November 2019 until recruitment into the MSS3 host trial ceases. The SWAT will adopt a factorial design, with patients randomised to one of four interventions. Potential participants invited by post to take part in MSS3 will receive the full contents of the standard recruitment pack (described at Stage 3 above), with the addition of the following:

- **Intervention 1**: A pen with the trial logo.
- **Intervention 2:** A pen with the trial logo and a brief PIS (provided in addition to the standard length PIS).
- Intervention 3: A brief PIS (provided in addition to the standard length PIS).
- **Intervention 4:** The standard contents only no additional interventions.

A code will be added to each expression of interest form identifying which of the above interventions were included in the pack.

## Inclusion and exclusion criteria- The SWAT

The SWAT will include all patients identified as potentially eligible for the MSS3 trial: there are no additional inclusion or exclusion criteria.

## The recruitment interventions

## The control intervention – the standard length PIS

The standard length PIS (Appendix B) was developed by the MSS3 host trial team, based at Sheffield CTRU, following National Research Ethics Service (NRES) guidance and will be reviewed by an NHS REC as part of the ethics application for the MSS3 study. The content of the PIS includes; general information about the purpose of the trial, how and why the participant might be involved, key trial concepts, such as randomization, the interventions being tested, and the potential risks and benefits of those interventions, participant's right to withdraw, trial team contact information, confidentiality information, and details on who is funding and monitoring the research. The information has been reviewed by the patient representative member of the MSS3 Trial Management Group and will also be reviewed by the Trial Steering Committee which also includes a patient representative. The standard PIS is 6 A4 pages in length. The accompanying GP invitation letter, the expression of interest form and the PHQ-15 will all be on single A4 sheets (Appendix D).

## The brief PIS

The brief PIS will consist of an A4 sized sheet printed on high quality paper in colour and folded into three, in a leaflet style. It has been designed to provide a more succinct and easy to read summary of the MSS3 trial than the standard PIS. The information has been reviewed by the patient representative on the MSS3 Trial Management Group. It will be provided alongside the standard PIS in the recruitment pack. The invitation letter will explain that the brief PIS is there in order to provide the patients with a summary of the research in order to decide if they might be interested in participating and that the standard PIS provides more details should

they wish to read this before returning the form, but that they will have the opportunity to discuss the study with a nurse and ask questions later.

Appendix C is the brief PIS.

## The pen intervention

The pens will be branded with the MSS3 "brief" logo and colours (see below). The pens will be black ink, of a good standard (mid-price) and similar to those used previously as promotional items on clinical trials managed by Sheffield CTRU.

## Randomisation

The type of intervention included in each invitation pack (whether a brief PIS and/or a pen is to be included or not) will be determined by random allocation. Patients will be randomised in a 1:1:1:1 ratio, stratified by GP practice. Block randomisation with random varying block sizes will be used, with the block sizes being determined by a statistician and not shared with other researchers. The allocation lists will be generated by a CTRU statistician and shared only with the CTRU staff preparing the invitation packs, who will be independent of the CTRU staff who will process the invitation responses. All recruitment materials will be placed in sealed envelopes which will be pre-stamped, ready for the practice to post out to patients. The packs will be placed in order of the random allocation list and then numbered sequentially before being sent to the practice. By numbering the packs, the researcher will have a record of which interventions are in each pack, which will enable the trial team to monitor if packs are sent out in the correct randomised order. Practice staff will be informed to label the sealed recruitment packs with patient addresses in the sequential order that the researcher had placed them in. Patients will not know that they are part of a trial testing recruitment interventions so will be blind to the SWAT hypothesis. CTRU staff undertaking trial recruitment will be blind to the group to which patients are allocated. It will not be possible to entirely blind practice staff to the interventions as it will be clear that some packs have pens in and some do not.

## **Outcome measures**

### Primary Outcome

1. The primary outcome is the effectiveness of the recruitment interventions. This is defined as the recruitment rate, being the proportions of participants in each intervention group who are randomised into the host trial.

### Secondary Outcomes

- 1. The proportion of patients in each intervention group who return an expression of interest form
- 2. The cost-effectiveness of the interventions for each host trial
- 3. The proportion of patients who return an expression of interest form but do not go on to be randomised due to a) ineligibility or b) non-consent, according to each intervention group
- 4. The time taken to respond to an invitation to participate in MSS3

## **Statistical methods**

## Sample size calculation

The sample size calculations for the MSS3 trial have been outlined in the main trial protocol. As is usual with a study within a trial, we did not undertake a formal power calculation to determine the sample size (19), since the sample size is constrained by the number of patients being approached in the MSS3 host trial. The sample size will therefore be the total number of patients invited into the MSS3 trial. Based on response rates achieved in two preliminary studies we estimate we will need to invite 4888 patients in order to recruit 376 to the trial, representing a recruitment rate of about 8%. This would provide 80% power to identify a 3% difference between the groups in recruitment rate if one existed. A simple multiple comparison adjustment was applied, using a significance level of 2.5%, which would allow us to test both interventions.

## Statistical analyses

Analyses will be conducted on an intention to treat basis, including all randomised participants on the basis of the groups to which they were randomised. Analysis will be conducted using 2 sided significance tests at the 5% significance level. For analysis of the primary outcome, logistic regression will be used to produce odds ratios and their associated 95% confidence intervals and p-values. Cost effectiveness will be presented as a cost-per-additional recruited participant.

Results from this SWAT will ultimately be combined in a meta-analysis with response rate data from other host trials participating in the PROMETHEUS study.

Anonymised data from MSS3 will be sent to the PROMETHEUS study team in accordance with the PROMETHEUS study data sharing agreement (Appendix E).

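### The recruitment sub-study (SWAT) sets 2.5% per intervention in its power statement but tests at 5% in its analysis section, so its multiplicity adjustment is never carried out

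*Protocol*

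**What the plan says.** All of this is in Appendix 1 of the protocol, which section 10.3 describes as the full protocol of the sub-study.

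- **Sample size calculation, significance level:** "A simple multiple comparison adjustment was applied, using a significance level of 2.5%, which would allow us to test both interventions".
- **Sample size calculation, power:** "This would provide 80% power to identify a 3% difference between the groups in recruitment rate if one existed". The basis is that "we estimate we will need to invite 4888 patients in order to recruit 376 to the trial". No formal calculation fixed the sample size, because the host trial decides how many patients are invited.
- **Statistical analyses, significance level:** "Analysis will be conducted using 2 sided significance tests at the 5% significance level".
- **Statistical analyses, primary outcome:** "logistic regression will be used to produce odds ratios and their associated 95% confidence intervals and p-values".
- **Randomisation:** "Patients will be randomised in a 1:1:1:1 ratio, stratified by GP practice". The design is factorial with four packs: pen, pen plus brief sheet, brief sheet, and standard contents only.

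**The concern.** The sample size paragraph presents 2.5% as the level that permits two tests, so it is a testing threshold and not only a planning input. The paragraph that governs the tests uses 5%, and its 95% intervals match 5%. An adjustment that appears in the power statement but not in the test controls nothing.

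Two things are at stake. The first is the family-wise error for the pen and brief-sheet comparisons. The second is that a p-value between 0.025 and 0.05 would be significant under one paragraph and not under the other. With both levels in the protocol, the choice could be made after the results are known. The sub-study is to be published in its own right as well as pooled, so its own p-values will be read.

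The power sentence has a smaller, related gap. It says neither which groups are compared nor whether the 3% is a rise or a fall, and in a four-pack factorial design the power depends heavily on both.

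**Working it through.** **Inputs (Appendix 1).** 4888 invited and 376 recruited, so 376/4888 = 7.69%, which the appendix rounds to about 8%. Allocation is 1:1:1:1, so 4888/4 = 1222 per pack and 4888/2 = 2444 per level of each factor. The significance level is 0.025 in the sample size paragraph and 0.05 in the analysis paragraph.

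**1. Family-wise error for two tests.** For independent tests this is 1 − (1 − α)²; the upper bound under any dependence is 2α.

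| Level per test | Independent tests | Upper bound |
|---|---|---|
| 0.025 (sample size paragraph) | 1 − 0.975² = 4.94% | 5% |
| 0.05 (analysis paragraph) | 1 − 0.95² = 9.75% | 10% |

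The ratio is 9.75/4.94 = 1.97, so the error rate roughly doubles.

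**2. Can the stated 80% be reproduced?** Two-sided normal approximation with pooled variance under the null:

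power = Φ[(|p₁ − p₂| − z·s₀)/s₁], where s₀ = √{p̄(1 − p̄)(1/n₁ + 1/n₂)}, s₁ = √{p₁(1 − p₁)/n₁ + p₂(1 − p₂)/n₂}, and z = 2.241 for α = 0.025.

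Single packs, 7.69% v 4.69%, n = 1222 each: p̄ = 0.0619, s₀ = 0.00975, s₁ = 0.00973. Then (0.03 − 2.241 × 0.00975)/0.00973 = 0.84, and Φ(0.84) gives 79.9%. So the figure does reproduce, for a fall between two packs.

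It also reproduces for a rise, comparing one pack with the other three (1222 v 3666): 79.1% for 8% v 11% and 80.4% for 7.69% v 10.69%.

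**3. Power for 3 points at α = 0.025 by comparison and direction.**

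| Comparison | Rates | Power |
|---|---|---|
| Factorial margins, 2444 v 2444 | 8% v 11% | 90.9% |
| Factorial margins, 2444 v 2444 | 7.69% v 10.69% | 91.8% |
| Factorial margins, 2444 v 2444 | 8% v 5% | 97.8% |
| Single packs, 1222 v 1222 | 8% v 11% | 61.3% |
| Single packs, 1222 v 1222 | 7.69% v 10.69% | 62.8% |
| Single packs, 1222 v 1222 | 8% v 5% | 77.9% |

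Worked example for the margins, 8% v 11%: p̄ = 0.095, s₀ = 0.00839, s₁ = 0.00838. Then (0.03 − 2.241 × 0.00839)/0.00838 = 1.34, and Φ(1.34) gives 90.9%.

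**4. Difference detectable with 80% power on the margins at α = 0.025.** From a reference rate of 7.69% to 8%: 2.5 to 2.6 points for a rise and 2.2 points for a fall.

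**5. If the adjustment were dropped.** At α = 0.05 (z = 1.960) the margins give 94.7% for 8% v 11% and 98.9% for 8% v 5%. Single packs give 71.6% for 8% v 11%.

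**The case against.** **On the significance level.** The pen and the brief sheet are separate questions, each with its own SWAT registration, done or planned. Leaving two factorial main effects unadjusted is a common and defensible choice. The appendix states no success rule: it reports odds ratios, intervals and p-values, and the data then go into a meta-analysis. This stands as an argument that 5% could be right, and it limits the practical consequence. It does not remove the conflict, because the appendix says that an adjustment was applied and why. If 5% was always intended, the power paragraph describes a test that will not be run.

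**On power.** A reader might infer that the stated 80% is an arithmetical error, or that it can be obtained only for a fall in recruitment. The documents support neither reading. The sentence names no groups and no direction, and about 80% is reproduced both for a fall between single packs and for a rise in one pack against three. On the factorial margins the detectable rise of 2.5 to 2.6 points also rounds to 3%, in a paragraph that rounds 7.69% to 8%. If the margins are meant, the sub-study has more power than it claims. What remains is that the comparison and direction are unstated.

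**On weight.** No sample size depends on the power figure, since the host trial fixes the number invited. That also stands.

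**Conclusion.** The conflict between 2.5% and 5% is real, and nothing else in the protocol resolves it. As written, the analysis runs two tests with a family-wise error of about 9.75% (bound 10%), where the sample size paragraph planned for about 4.9% (bound 5%).

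The power figure is under-specified, not shown to be wrong. For 3 points at 2.5% it is conservative on the factorial margins (about 91% to 98%), but too high if single packs are compared and a rise from 7.7% to 8% is meant (about 61% to 63%).

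Assumptions: two tests, one per intervention; independence for the 9.75% and 4.9% figures (the bounds need none); the 3% read as absolute percentage points; a reference rate of 7.69% to 8%; no interaction between pen and brief sheet; stratification by practice ignored.

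This is a minor internal inconsistency. It is confined to the recruitment sub-study and does not touch the MSS3 primary outcome or its analysis.

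**What to change.** **Significance level.** Preferred: amend the Statistical analyses paragraph of Appendix 1 so that each of the two main effects on the primary outcome is tested at two-sided 2.5% with a 97.5% confidence interval, as the sample size paragraph already intends. The cost is a stricter threshold for each factor. Alternative: keep 5% and 95% intervals, remove the adjustment from the sample size paragraph, say openly that the two questions are tested without adjustment, and restate the power at 5% (about 95% for 8% v 11% and 99% for 8% v 5% on the margins). The cost is a family-wise error of up to 10%.

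**Power statement.** Name the groups and the direction. For main effects at 2.5%, for example: with 2444 per level, power for a 3-point difference is about 91% (8% v 11%) to 98% (8% v 5%), and 80% power is reached at about 2.2 to 2.6 points depending on direction. If single packs are meant, say so and give about 61% to 63% for a 3-point rise.

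Either route is about two sentences. Neither changes the number invited, the allocation or anything in the host trial, and the choice is best recorded before the sub-study data are analysed.

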# **Ethical issues**

Research Ethics Committee (REC) and Health Research Authority approval for the host trial was sought from Greater Manchester Central Research Ethics Committee on 25th June 2018. This SWAT was submitted as part of the main trial, to enable the recruitment interventions to be implemented in the host trial setting.

Patients will not be informed about this recruitment SWAT and so will not have the opportunity to give informed consent. Patients will therefore be blind to the SWAT allocation. In this case of evaluating whether a pen and/or brief PIS impact on recruitment rates, seeking individual patient consent prior to sending the invitation is not appropriate. This is because it may confuse patients as to what they are consenting to, and may impact on their behaviour if they are aware that different recruitment methods are being tested, confounding the evaluation (20).

# **SWAT registration**

The pen SWAT has been registered on the MRC SWATs database as SWAT 37. The brief PIS will also be registered as a sub-study on the MRC SWATs database.

# **Financial and Insurance Issues**

The SWAT is funded as part of the PROMETHEUS programme, which is sponsored by the University of York. It forms a sub-study to the MSS3 trial, which is sponsored by NHS Sheffield Clinical Commissioning Group.

Date	Action
27 th April 2018	Documentation for the SWAT agreed & signed off
11 th May 2018	Submission to REC of application
1 st October 2018	Recruitment to the SWAT begins

# **Project Timetable**

1 st November 2019	Recruitment to the SWAT ends
1 st February 2020	Data cleaning and submission of data set to PROMETHEUS team
1 st April 2020	Collation of results and analysis, begin write up of trial level paper

# **Dissemination of research**

The results of this SWAT will be published in a peer-reviewed journal to further improve the evidence base regarding effective recruitment strategies in trials. This publication will be led by the MSS3 team, with input from PROMETHEUS members. In addition the data will be included in a meta-analysis of all studies of the same intervention conducted by the PROMETHEUS programme led by the PROMETHEUS team. Dissemination of research findings will be conducted in line with the PROMETHEUS authorship arrangements (Appendix F).

# Appendices

Appendix A: Flow of participants through MSS3

Appendix B: Standard participant information sheet

Appendix C: Brief participant information sheet

Appendix D: GP invitation letter, the expression of interest form and the PHQ-15

Appendix E: PROMETHEUS Data sharing agreement

Appendix F: PROMETHEUS publications & authorship arrangements

#### Appendix A: Flow of participants through MSS3

Appendix B: Standard participant information sheet (over page)

## PHYSICAL SYMPTOMS (PHQ-15)

During the past 4 weeks, how much have you been bothered by any of the following problems?

	Not bothered at all (0)	Bothered a little (1)	Bothered a lot (2)
a. Stomach pain			
b. Back pain			
c. Pain in your arms, legs, or joints (knees, hips, etc.)			
d. Menstrual cramps or other problems with your periods WOMEN ONLY			
e. Headaches			
f. Chest pain			
g. Dizziness			
h. Fainting spells			
i. Feeling your heart pound or race			
j. Shortness of breath			
k. Pain or problems during sexual intercourse			
I. Constipation, loose bowels, or diarrhea			
m. Nausea, gas, or indigestion			
n. Feeling tired or having low energy			
o. Trouble sleeping			

(For office coding: Total Score T = + )

Developed by Drs. Robert L. Spitzer, Janet B.W. Williams, Kurt Kroenke and colleagues, with an educational grant from Pfizer Inc. No permission required to reproduce, translate, display or distribute.

Appendix E: PROMETHEUS Data sharing agreement

# **PROMETHEUS** Data sharing agreement

This document specifies the data management and data sharing agreement between the PROMETHEUS programme and the Multiple Symptoms Study 3 (MSS3) trial. In this document, the 'PROMETHEUS programme team' refers to researchers named on the PROMETHEUS protocol. 'PROMETHEUS collaborators' refers to those providing 'host' trials for the PROMETHEUS programme.

